4 STUDY DESIGN

4.1 Study Overview

This is a single center, double-blind, randomized, 2 period crossover trial. We propose a sample size of 30. Following a five-day run-in period, during which participants will self-administer 0.9% normal saline by nebulizer three times per day, each participant will be randomized to receive a nebulized dose of study drug three times per day for seven days of either 20% NAC (active) or 0.9% saline (placebo). Following a 28-day washout period, participants will be switched to the alternate group for 7 days of treatment. Participants will be assigned to the treatments in random order. Evaluations will be taken at baseline, end of run-in, start of second treatment period, and at the end of each 7-day treatment period.

Screening data will be reviewed to determine participant eligibility. Participants who meet all inclusion criteria and none of the exclusion criteria will be entered into the study.

The following treatment regimens will be used:

- Experimental treatment of NAC 20%
- Placebo treatment of 0.9% saline

Total duration of participation will be nine weeks. Total duration of the study is expected to be 2 years.

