5 CRITERIA FOR EVALUATION

5.1 Primary Efficacy Endpoint

We used FEV1 measures from 219 adults with asthma published in Corren et al. NEJM, 2011¹. The authors found that the standard deviation for the change in FEV1 in liters from day 1 to day 7 was 19%. Using a standard deviation of 19 and a two-sided alpha of 0.05, we calculate a sample size of 30 to have 80% power to detect a change in FEV1 of 10% (a reasonable effect size because early studies of Pulmozyme in CF reported a 10% increase in FEV1 at day 3 of treatment)⁷.

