14.3 Analysis of Primary Endpoint

The primary outcome is the % change in FEV1 from the start to the end of the treatment period (either placebo or 20% NAC). The first analysis will be to test the assumption of negligible carryover effects from study period 1 to period 2. We will compare the sum of the outcome values measured in the two periods for each participant across the 2 sequence groups (placebo-20% vs. 20%-placebo) using an unpaired t-test. After no or negligible carryover effect has been confirmed, we will test for the difference in treatment effects between placebo and 20% NAC using a paired t-test.

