14.4 Analysis of Secondary Endpoints

As a secondary outcome, we will include an analysis that examines the change associated with the 7-day treatment with 0.9% saline. Our secondary analysis is to determine the characteristics of participants that respond to NAC. We will classify participants in four groups based on their post-bronchodilator FEV1 in response to NAC. FEV1 of 0-4% change will define non-responders and FEV1 of 5-9%, 10-14%, or > 15% will define the 3 categories of responders. We will examine NAC responders and non-responders to determine if baseline CT mucus scores, lung function measures, or sputum G' measures predict treatment response. We will construct ROC curves to determine the CT score that predicts NAC response thereby identifying a CT biomarker for future thiol saccharide trials. In addition, we will examine how the CT mucus score changes with NAC treatment using a subset of the participants following second period treatment. Finding a decrease in CT score in the 20% NAC group compared to the placebo group will provide support for

 our hypothesis that NAC improves lung function by decreasing intraluminal mucus. Other analyses will be to examine the effects of treatment on sputum elasticity (G').

Safety and tolerability data will be summarized by treatment group.

Adverse event rates will be coded by body system and MedDra classification term. Adverse events will be tabulated by treatment group and will include the number of patients for whom the event occurred, the rate of occurrence, and the severity and relationship to study drug.

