14.6 Sample Size and Randomization

We propose a sample size of 30, which will provide us with the power to examine the effect of NAC in a subgroup of individuals with asthma who have CT evidence of intraluminal mucus and to identify the CT mucus score that performs best as a biomarker of treatment response to NAC. Participants will be enrolled if their CT mucus scores are >3.0. To calculate sample size for the one-week treatment period study, we used FEV1 measures from 219 adults with asthma published in Corren et al. NEJM, 2011¹. The authors found that the standard deviation for the change in FEV1 in liters from day 1 to day 7 was 19%. Using a standard deviation of 19 and a two-sided alpha of 0.05, we calculate a sample size of 30 to have 80% power to detect a change in FEV1 of 10% (a reasonable effect size because early studies of Pulmozyme in CF reported a 10% increase in FEV1 at day 3 of treatment).

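### The 80% power at n=30 uses 19, described as the SD of one 7-day change, but the primary test is on a paired difference; if 19 is the per-period SD, 80% needs an unstated within-person correlation of about 0.5 or more

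*Combined protocol and SAP*

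**What the plan says.** Section 14.6 takes its variability input from a published trial in 219 adults with asthma: "The authors found that the standard deviation for the change in FEV1 in liters from day 1 to day 7 was 19" percent. From this and a two-sided alpha of 0.05 it concludes: "we calculate a sample size of 30 to have 80% power to detect a change in FEV1 of 10" percent. The effect size is called "a reasonable effect size because early studies of Pulmozyme in CF reported a 10% increase in FEV1 at day 3 of treatment". Section 5.1 and the synopsis repeat the calculation ("Using a standard deviation of 19 and a two-sided alpha of 0.05, we calculate a sample size of 30").

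The design in 4.1 is a two-period crossover. After washout, "participants will be switched to the alternate group for 7 days of treatment", so each participant contributes one change on NAC and one on placebo. Section 14.3 defines the outcome within a period ("The primary outcome is the % change in FEV1 from the start to the end of the treatment period") and then compares the treatments: "we will test for the difference in treatment effects between placebo and 20% NAC using a paired t-test".

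No section states an SD for the NAC-minus-placebo difference, a correlation between the two period changes, or any conversion from 19 to the paired scale.

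**The concern.** A paired t-test is powered by the SD of the within-person difference. Section 14.6 describes the SD of one change over one interval, which is a different quantity. The two are equal only under a particular correlation between a person's two changes, and the plan does not mention one. The relevant correlation is between the two 7-day changes, not between raw FEV1 values.

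Three further points leave the inputs unclear:

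- **Units.** The SD is attached both to litres and to a percentage, while the primary outcome is a percentage change.
- **Meaning of the 10%.** It is justified by an on-treatment increase in another disease, so it may mean the change on NAC alone. In that case 19 is the matching SD, but the 80% then describes a test of one arm against zero, and the primary comparison has no stated power.
- **Equal SDs.** Any conversion also needs the SD on NAC and on placebo. Section 14.4 expects response to NAC to vary between people ("We will classify participants in four groups based on their post-bronchodilator FEV1 in response to NAC"), so equality cannot be taken for granted.

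This is the only power figure in the plan. If it is not tied to the primary test, a reader of a null result cannot tell whether the trial had about 50% or about 90% power for the effect it planned to detect.

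**Working it through.** **Inputs from 14.6 and 14.3:** n = 30, two-sided alpha 0.05, effect 10 percentage points, SD 19, paired t-test. All values of rho, and all SDs other than 19, are assumptions because the documents give none.

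**1. Reproduce the plan's figure.** Enter 19 directly as the SD of the analysed quantity.

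- Normal approximation: n = (19 × (1.960 + 0.842) / 10)² = 28.3, rounded up to 29. Power at n = 30 is 82.2%.
- Exact t: the non-centrality parameter is 10 × √30 / 19 = 2.88 on 29 df. Power is 79.6%, and 31 participants are needed to reach 80%.
- Alternatives do not give 30. One-sided alpha gives 23, and a two-sample comparison gives 57 per arm.

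So 19 was treated either as the SD of the paired difference or as the SD of a single change tested against zero.

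**2. Largest paired-difference SD compatible with 80% power.** At n = 30 and 10 points it is 18.9 (exact t) or 19.55 (normal approximation).

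**3. Take 19 as described, as the per-period SD, equal under both treatments.** Then

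SD_diff = √(19² + 19² − 2·rho·19²) = 19 × √(2(1 − rho)).

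This equals 19 only at rho = 0.5. Exact t results at n = 30:

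| Assumed rho | SD_diff | Power for 10 points | Difference detectable with 80% power |
|---|---|---|---|
| 0 | 26.87 | 50% | 14.2 |
| 0.2 | 24.03 | 60% | 12.7 |
| 0.4 | 20.81 | 72% | 11.0 |
| 0.5 | 19.00 | 80% (79.6%) | 10.1 |
| 0.6 | 16.99 | 88% | 9.0 |
| 0.7 | 14.72 | 95% | 7.8 |

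The smallest rho giving 80% is 1 − 18.895² / (2 × 19²) = 0.51 (exact t), or 0.47 by the normal approximation. At rho = 0, 80% power would need 59 participants (exact t). Using 28 df, to allow for a period effect, changes power by about 0.1 point.

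**4. Sensitivity to the SD (assumed values).**

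- Unequal SDs, SD_diff = √(a² + b² − 2·rho·a·b), at rho = 0.5: 19 and 15 give 17.35 and 86% power (rho floor 0.40); 19 and 22 give 20.66 and 73% (floor 0.58); 19 and 25 give 22.61 and 65% (floor 0.66).
- Common per-period SD s, floor = 1 − 18.895² / (2s²): 0.01 at 13.4, 0.21 at 15, 0.38 at 17 and 0.60 at 21.

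**The case against.** The best defence is that no sum is wrong: SD 19, 10 points and n = 30 do give about 80%. With equal SDs, entering 19 directly is algebraically the same as assuming rho = 0.5, so the plan is compatible with one simple unwritten assumption. It is also possible that 19 was meant as the SD of the paired difference; the sentence is garbled, and only the cited trial could settle it.

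Nothing in the documents supports rho = 0, and some features point to a positive rho. Section 8.1.2 applies medication withholding at Visits 5 and 8, the two end-of-period visits, but not at the start visits 4 and 7. Any person-specific effect of withholding would therefore enter both changes. Stable background medication and the run-in with its adherence requirement could also make the SD smaller than in the source trial, which would lower the floor for rho. On this view the point is a clarification, and one sentence would settle it.

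Much of this stands. It is right that a shortfall in power is not shown, that 50% is one end of an assumed range, and that a smaller per-period SD would relax the requirement. But the defence confirms the gap. The 80% depends on rho of about 0.5, or on a reading of 19 that differs from the plan's own description, and neither is written down. The arguments for a positive rho are inferences with no size attached.

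**Conclusion.** The concern holds. The stated 80% does not follow from the plan's inputs as described, because 19 is presented as the SD of a single 7-day change while the primary test analyses the difference between two of them. If 19 is the per-period SD under both treatments, 80% power at n = 30 needs rho of at least 0.51 (exact t) or 0.47 (normal approximation). Power for a 10-point difference ranges from 50% to 95% over assumed rho of 0 to 0.7. If 19 is in fact the SD of the paired difference, about 80% stands.

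Confidence is high on the mismatch and the missing assumption. It does not extend to any value of rho, nor to a claim that 30 participants are too few. Because this is the plan's only power figure and it is attached to the primary comparison, it should be corrected and not left to inference.

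**What to change.** In 14.6, 5.1 and the synopsis:

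1. Say whether 19 is the SD of a single-period percentage change or of the NAC-minus-placebo difference. Resolve the litres/percent wording, and say whether the 10% is the treatment difference tested in 14.3.
2. State the assumed rho, or the SD of the paired difference, and its basis.
3. Replace the unqualified 80% with a conditional statement. If 19 is confirmed as the per-period SD, suitable text would be:

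> With n=30, two-sided alpha 0.05 and a per-period SD of 19 under both treatments, power to detect a 10-point NAC-minus-placebo difference is 50%, 60%, 72%, 80% and 88% for within-person correlations of 0, 0.2, 0.4, 0.5 and 0.6 (detectable difference with 80% power 14.2, 12.7, 11.0, 10.1 and 9.0 points).

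Naming the planning value of rho from item 2 beside this range keeps a clear design assumption. If 19 is the SD of the paired difference, say so and give its source; about 80% can then stay.

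The cost is wording in three places. The sample size, conduct, primary outcome, test and type I error do not change. The downside is that the stated power becomes conditional and possibly less favourable.

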15 DATA COLLECTION, RETENTION AND MONITORING

15.1 Data Collection Instruments

The Investigator will prepare and maintain adequate and accurate source documents designed to record all observations and other pertinent data for each participant treated with the study drug.

Study personnel at each site will enter data from source documents corresponding to a participant's visit into the protocol-specific paper CRF when the information corresponding to that visit is available. Participants will not be identified by name in the study database or on any study documents to be collected by the Sponsor (or designee), but will be identified by a site number, participant number and initials.

The Investigator is responsible for all information collected on participants enrolled in this study. All data collected during the course of this study must be reviewed and verified for completeness and accuracy by the Investigator. A copy of the CRF will remain at the Investigator's site at the completion of the study.

15.2 Data Management Procedures

The data will be entered into a validated database. The Data Management group will be responsible for data processing, in accordance with procedural documentation. Database lock will occur once quality assurance procedures have been completed.

All procedures for the handling and analysis of data will be conducted using good computing practices meeting FDA guidelines for the handling and analysis of data for clinical trials.

15.3 Data Quality Control and Reporting

After data have been entered into the study database, a system of computerized data validation checks will be implemented and applied to the database on a regular basis. Query reports (Data Clarification Requests) pertaining to data omissions and discrepancies will be forwarded to the clinical research coordinators for resolution. The study database will be updated in accordance with the resolved queries. All changes to the study database will be documented.

15.4 Archival of Data

The database is safeguarded against unauthorized access by established security procedures; appropriate backup copies of the database and related software files will be maintained. Databases are backed up by the database administrator in conjunction with any updates or changes to the database.

At critical junctures of the protocol (e.g., production of interim reports and final reports), data for analysis is locked and cleaned per established procedures.

15.5 Availability and Retention of Investigational Records

The Investigator must make study data accessible to the monitor, other authorized representatives of the Sponsor (or designee), IRB/IEC, and Regulatory Agency (e.g., FDA) inspectors upon request. A file for each participant must be maintained that includes the signed Informed Consent, HIPAA Authorization and Assent Form and copies of all source documentation related to that participant. The Investigator must ensure the reliability and availability of source documents from which the information on the CRF was derived.

All study documents (patient files, signed informed consent forms, copies of CRFs, Study File Notebook, etc.) must be kept secured for a period of two years following marketing of the investigational product. There may be other circumstances for which the Sponsor is required to maintain study records and, therefore, the Sponsor should be contacted prior to removing study records for any reason.

15.6 Monitoring

Monitoring visits will be conducted by representatives of the Sponsor according to the U.S. CFR Title 21 Parts 50, 56, and 312 and ICH Guidelines for GCP (E6). By signing this protocol, the Investigator grants permission to the Sponsor (or designee), and appropriate regulatory authorities to conduct on-site monitoring and/or auditing of all appropriate study documentation.

Version #:1.5 Version Date: 8/5/2016 Page 35 of 41

15.7 Participant Confidentiality

In order to maintain participant confidentiality, only a site number, participant number and participant initials will identify all study participants on CRFs and other documentation. Additional participant confidentiality issues (if applicable) are covered in the Clinical Study Agreement.

16 ADMINISTRATIVE, ETHICAL, REGULATORY CONSIDERATIONS

The study will be conducted according to the Declaration of Helsinki, Protection of Human Volunteers (21 CFR 50), Institutional Review Boards (21 CFR 56), and Obligations of Clinical Investigators (21 CFR 312).

To maintain confidentiality, all laboratory specimens, evaluation forms, reports and other records will be identified by a coded number and initials only. All participant interviews/visits are conducted in private testing rooms. Information about study participants is kept in binders in a locked storage closet, and in our password protected secure electronic files, and is only accessible to authorized study personnel. Clinical information will not be released without written permission of the participant, except as necessary for monitoring by the FDA. The Investigator must also comply with all applicable privacy regulations (e.g., Health Insurance Portability and Accountability Act of 1996, EU Data Protection Directive 95/46/EC).

16.1 Protocol Amendments

Any amendment to the protocol will be written by the Sponsor. Protocol amendments cannot be implemented without prior written IRB/IEC approval except as necessary to eliminate immediate safety hazards to patients. A protocol amendment intended to eliminate an apparent immediate hazard to patients may be implemented immediately, provided the IRBs are notified within five working days.

16.2 Institutional Review Boards and Independent Ethics Committees

The protocol and consent form will be reviewed and approved by the IRB/IEC of each participating center prior to study initiation. Serious adverse experiences regardless of causality will be reported to the IRB/IEC in accordance with the standard operating procedures and policies of the IRB/IEC, and the Investigator will keep the IRB/IEC informed as to the progress of the study. The Investigator will obtain assurance of IRB/IEC compliance with regulations.

Any documents that the IRB/IEC may need to fulfill its responsibilities (such as protocol, protocol amendments, Investigator's Brochure, consent forms, information concerning patient recruitment, payment or compensation procedures, or other pertinent information) will be submitted to the IRB/IEC. The IRB/IECs written unconditional approval of the study protocol and the informed consent form will be in the possession of the Investigator before the study is initiated. The IRB/IECs unconditional approval statement will be transmitted by the Investigator to prior to the shipment of study supplies to the site. This approval must refer to the study by exact protocol title and number and should identify the documents reviewed and the date of review.

Version #:1.5 Version Date: 8/5/2016 Page 36 of 41

Protocol and/or informed consent modifications or changes may not be initiated without prior written IRB/IEC approval except when necessary to eliminate immediate hazards to the patients or when the change(s) involves only logistical or administrative aspects of the study. Such modifications will be submitted to the IRB/IEC and written verification that the modification was submitted and subsequently approved should be obtained.

The IRB/IEC must be informed of revisions to other documents originally submitted for review; serious and/or unexpected adverse experiences occurring during the study in accordance with the standard operating procedures and policies of the IRB; new information that may affect adversely the safety of the patients of the conduct of the study; an annual update and/or request for re-approval; and when the study has been completed.

16.3 Informed Consent Form

Informed consent will be obtained in accordance with the Declaration of Helsinki, ICH GCP, US Code of Federal Regulations for Protection of Human Subjects (21 CFR 50.25[a,b], CFR 50.27, and CFR Part 56, Subpart A), the Health Insurance Portability and Accountability Act (HIPAA, if applicable), and local regulations.

The Investigator will prepare the informed consent form, assent and HIPAA authorization and provide the documents to the IRB/IEC for approval prior. The consent form generated by the Investigator must be approved by the IRB/IEC. The written consent document will embody the elements of informed consent as described in the International Conference on Harmonisation and will also comply with local regulations.

A properly executed, written, informed consent will be obtained from each participant prior to entering the participant into the trial. Information should be given in both oral and written form and participants must be given ample opportunity to inquire about details of the study. A copy of the signed consent form will be given to the participant and the original will be maintained with the participant's records.

16.4 Publications

The preparation and submittal for publication of manuscripts containing the study results shall be in accordance with a process determined by mutual written agreement among the study Sponsor and participating institutions. The publication or presentation of any study results shall comply with all applicable privacy laws, including, but not limited to, the Health Insurance Portability and Accountability Act of 1996.

16.5 Investigator Responsibilities

By signing the Agreement of Investigator form, the Investigator agrees to:

- 1. Conduct the study in accordance with the protocol and only make changes after notifying the Sponsor (or designee), except when to protect the safety, rights or welfare of participants.
- 2. Personally conduct or supervise the study (or investigation).
- 3. Ensure that the requirements relating to obtaining informed consent and IRB review and approval meet federal guidelines, as stated in § 21 CFR, parts 50 and 56.

Version #:1.5 Version Date: 8/5/2016 Page 37 of 41

- 4. Report to the Sponsor or designee any AEs that occur in the course of the study, in accordance with §21 CFR 312.64.
- 5. Ensure that all associates, colleagues and employees assisting in the conduct of the study are informed about their obligations in meeting the above commitments.
- 6. Maintain adequate and accurate records in accordance with §21 CFR 312.62 and to make those records available for inspection with the Sponsor (or designee).
- 7. Ensure that an IRB that complies with the requirements of §21 CFR part 56 will be responsible for initial and continuing review and approval of the clinical study.
- 8. Promptly report to the IRB and the Sponsor (or designee) all changes in the research activity and all unanticipated problems involving risks to participants or others (to include amendments and IND safety reports).
- 9. Seek IRB approval before any changes are made in the research study, except when necessary to eliminate hazards to the patients/ participants.
- 10. Comply with all other requirements regarding the obligations of clinical investigators and all other pertinent requirements listed in § 21 CFR part 312.

Version #:1.5 Version Date: 8/5/2016 Page 38 of 41

